8.3 Pregnancies

To ensure patient safety, each pregnancy occurring while the patient is on study treatment must be reported to Novartis within 24 hours of learning of its occurrence. The pregnancy should be followed up to determine outcome, including spontaneous or voluntary termination, details of the birth, and the presence or absence of any birth defects, congenital abnormalities, or maternal and/or newborn complications.

Pregnancy should be recorded on a Clinical Trial Pregnancy Form and reported by the investigator to the oncology Novartis Patient Safety. Pregnancy follow-up should be recorded on the same form and should include an assessment of the possible relationship to the study treatment any pregnancy outcome. Any SAE experienced during pregnancy must be reported on the SAE Report Form.

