7.2.2.4.5 Pregnancy and assessments of fertility

For pre- or perimenopausal patients, a serum or urine pregnancy tests (patients who have undergone a hysterectomy do not need pregnancy tests performed) are to be performed according to the Visit Schedules outlined in [Table 7-1](#). At screening, a serum pregnancy test should be performed for pre- and perimenopausal patients, regardless of the age of the patients, while at baseline, during the study, and at the end of trial, urinary pregnancy tests are sufficient. Simultaneously, FSH and/or estradiol should be measured to ensure postmenopausal status.

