8.1 Adverse events

8.1.1 Definitions and reporting

An adverse event is defined as the appearance of (or worsening of any pre-existing) undesirable sign(s), symptom(s), or medical condition(s) that occur after patient's signed informed consent has been obtained.

Abnormal laboratory values or test results occurring after informed consent constitute adverse events only if they induce clinical signs or symptoms, are considered clinically significant, require therapy (e.g., hematologic abnormality that requires transfusion or hematological stem cell support), or require changes in study medication(s).

Adverse events that begin or worsen after informed consent should be recorded in the Adverse Events CRF. Conditions that were already present at the time of informed consent should be recorded in the Medical History page of the patient's CRF. Adverse event monitoring should be continued for at least 30 days (or 5 half-lives, whichever is longer) following the last dose of study treatment. Adverse events (including lab abnormalities that constitute AEs) should be described using a diagnosis whenever possible, rather than individual underlying signs and symptoms. When a clear diagnosis cannot be identified, each sign or symptom should be reported as a separate Adverse Event.

Adverse events will be assessed according to the Common Terminology Criteria for Adverse Events (CTCAE) version 4.03. If CTCAE grading does not exist for an adverse event, the severity of mild, moderate, severe, and life-threatening, corresponding to Grades 1 - 4, will be used. CTCAE Grade 5 (death) will not be used in this study. If death is not caused by progression of the disease, it has to be reported as SAE on the SAE report form. Adverse events with death as outcome must be documented as SAE on the SAE report form.

The occurrence of adverse events should be sought by non-directive questioning of the patient (subject) during the screening process after signing informed consent and at each visit during the study. Adverse events also may be detected when they are volunteered by the patient (subject) during the screening process or between visits, or through physical examination, laboratory test, or other assessments.

As far as possible, each adverse event should be evaluated to determine:

- The severity grade (CTCAE Grade 1-4).
- Its duration (Start and end dates).
- Its relationship to the study drug (Yes or No).

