8.2 Serious adverse events

8.2.1 Definitions

Serious adverse event (SAE) is defined as one of the following:

- Is fatal or life-threatening.
- Results in persistent or significant disability/incapacity.
- Constitutes a congenital anomaly/birth defect.
- Is medically significant, i.e., defined as an event that jeopardizes the patient or may require medical or surgical intervention to prevent one of the outcomes listed above.
- Requires inpatient hospitalization or prolongation of existing hospitalization,
- **Note:** Hospitalizations for the following reasons should not be reported as serious adverse events:
 - Routine treatment or monitoring of the studied indication, not associated with any deterioration in condition.
 - Elective or pre-planned treatment for a pre-existing condition that is unrelated to the indication under study and has not worsened since signing the informed consent.
 - Social reasons and respite care in the absence of any deterioration in the patient's general condition.
- **Note:** Treatment on an emergency outpatient basis that does not result in hospital admission and involves an event not fulfilling any of the definitions of a SAE given above is not a serious adverse event.

Protocol exempt SAEs

SAEs specifically defined in the protocol and where there has been a clear agreement with regulators not to collect these SAEs in the safety database, provided the information is collected elsewhere. In this existing protocol, progression of malignancy (including progression of malignancy with fatal outcome).

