8.2.2 Reporting

To ensure patient safety, every SAE, regardless of suspected causality, occurring after the patient has provided informed consent and until 30 days after the patient has stopped study drug must be reported to Novartis within 24 hours of learning of its occurrence.

Any SAEs experienced after this 30-day period should only be reported to Novartis if the investigator suspects a causal relationship to the study treatment (ribociclib, letrozole and/or goserelin).

Recurrent episodes, complications, or progression of the initial SAE must be reported as follow-up to the original episode, regardless of when the event occurs. This report must be submitted within 24 hours of the investigator receiving the follow-up information. An SAE that is considered completely unrelated to a previously reported one should be reported separately as a new event.

Information about all SAEs is collected and recorded on the Serious Adverse Event Report Form; all applicable sections of the form must be completed in order to provide a clinically thorough report. The investigator must assess and record the relationship of each SAE to each specific study treatment (if there is more than one study treatment), complete the SAE Report Form in English, and send the completed, signed form by fax within 24 hours to the oncology Novartis Patient Safety department.

The telephone and telefax number of the contact persons in the local department of Novartis Patient Safety, specific to the site, are listed in the investigator folder provided to each site.

The original copy of the SAE Report Form and the fax confirmation sheet must be kept with the case report form documentation at the study site.

Follow-up information is sent to the same contact(s) to whom the original SAE Report Form was sent, using a new SAE Report Form stating that this is a follow-up to the previously reported SAE and giving the date of the original report. Each re-occurrence, complication, or progression of the original event should be reported as a follow-up to that event regardless of when it occurs. The follow-up information should describe whether the event has resolved or continues, if and how it was treated, and whether the patient continued or withdrew from study participation.

An SAE that is considered completely unrelated to a previously reported one should be reported separately as a new event.

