11.3 Informed consent procedures

Eligible patients may only be included in the study after providing written (witnessed, where required by law or regulation), IRB/IEC/REB-approved informed consent.

Informed consent must be obtained before conducting any study-specific procedures (i.e. all of the procedures described in the protocol). The process of obtaining informed consent should be documented in the patient source documents. The date when a subject's Informed Consent was actually obtained will be captured in their CRFs.

Novartis will provide to investigators, in a separate document, a proposed informed consent form (ICF) that is considered appropriate for this study and complies with the ICH GCP guideline and regulatory requirements. Any changes to this ICF suggested by the investigator must be agreed to by Novartis before submission to the IRB/IEC/REB, and a copy of the approved version must be provided to the Novartis monitor after IRB/IEC/REB approval.

Women of child bearing potential should be informed that taking the study medication may involve unknown risks to the fetus if pregnancy were to occur during the study and agree that in order to participate in the study they must adhere to the contraception requirement for the duration of the study. If there is any question that the patient will not reliably comply, they should not be entered in the study.

Additional consent form

Sub-studies and studies with an optional Exploratory Biomarker component will have a separate consent form covering those studies. This informed consent form will be submitted for ethical approval together with the Study Protocol and the main informed consent form of the Study. If a subject opts not to participate in the optional assessments, this in no way affects the subject's ability to participate in the main research study.

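### Section 8.3 does not clearly require a report of a pregnancy conceived after the last dose, although AE and SAE follow-up runs to 30 days

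*Protocol*

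**What the plan says.** Protocol section 8.3 requires that "each pregnancy occurring while the patient is on study treatment must be reported to Novartis within 24 hours of learning of its occurrence". The next sentence asks for outcome follow-up of that pregnancy, including birth details, defects and complications. A second paragraph asks for pregnancies to be recorded on a Clinical Trial Pregnancy Form and names no period. It also says: "Any SAE experienced during pregnancy must be reported on the SAE Report Form".

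The glossary places discontinuation of study treatment at the point where the patient stops taking it permanently. The follow-up sections (7.1.4 and 7.1.5) list AEs and SAEs, new anticancer therapy, tumour evaluation, progression and survival. They do not mention pregnancy.

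Other safety windows run past the last dose:

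- AE monitoring (8.1.1) continues for "at least 30 days (or 5 half-lives, whichever is longer) following the last dose of study treatment".
- SAEs are reported whatever the cause until 30 days after study drug is stopped (8.2.2). After that: "Any SAEs experienced after this 30-day period should only be reported to Novartis if the investigator suspects a causal relationship".
- Sexually active men must use a condom and not father a child until 21 days after stopping (note to the exclusion criteria, 5.3).

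**The concern.** Section 11.3 has women of child-bearing potential told that "taking the study medication may involve unknown risks to the fetus". Unknown fetal risk is a reason to collect every exposed pregnancy prospectively, normal outcomes included. If the duty stops with the last dose, a conception shortly afterwards, with drug still in the body, falls outside the clear part of the rule. Whether the sponsor learns of it, and whether the outcome is followed, would depend on how the site reads 8.3, on its initiative, or on a later causality judgement. What is at stake is the completeness of pregnancy safety data, not any efficacy result.

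**Working it through.** **Inputs.** Effective half-lives from Table 1-3 (600 mg ribociclib with letrozole): ribociclib 32.5 ± 12.5 h, letrozole 77.3 ± 36.6 h. Stated terminal half-life of letrozole (1.2.2): 2 days. Five half-lives is the convention in 8.1.1.

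**Reproducing the printed half-lives.** With 24-hour dosing and accumulation ratio R, the effective half-life is ln 2 × 24 / ln(R/(R − 1)).

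- Letrozole, R = 5.2: 77.9 h (printed 77.3).
- Ribociclib, R = 2.4: 30.9 h (printed 32.5). The 5% difference is what one expects if the printed value is a mean of per-patient values on a slightly different n.
- First-in-human range (1.2.1.2.3), R = 1.35 and 3.11: 12.3 h and 42.9 h, matching the printed 12.3 and 42.9. No unit is printed there; the match shows that it is hours.

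**Time to five half-lives** = 5 × half-life in hours / 24, then as a share of 30 days.

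- Ribociclib: 5 × 32.5 / 24 = 6.8 days (23%).
- Letrozole, 2 days: 5 × 48 / 24 = 10.0 days (33%).
- Letrozole, 77.3 h: 5 × 77.3 / 24 = 16.1 days (54%).
- Letrozole, +1 SD (77.3 + 36.6 = 113.9 h): 5 × 113.9 / 24 = 23.7 days (79%).

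All fall within 30 days. The share of letrozole left at day 30, 2^(−720/half-life), is 0.003%, 0.16% and 1.25% for the three values in turn.

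**Effect of the rest week.** After a full course the last ribociclib dose is on day 21, and 21 + 6.8 = 27.8. Washout then ends in the day 22 to 28 break, while letrozole continues and the patient is still on study treatment. Ribociclib adds to the post-treatment window only if treatment stops earlier in the cycle. Letrozole is taken every day, so it sets the window.

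**Taking a post-dose conception through the rules.**

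- 8.3, first sentence: not covered if treatment ends at permanent stop.
- 8.2.1: pregnancy is not itself an SAE. A birth defect is ("Constitutes a congenital anomaly/birth defect"), but from a post-dose conception it would normally be seen long after day 30, when a report requires suspected causality.
- 8.3, SAE sentence: covers a serious event during the pregnancy, not the pregnancy or a normal outcome.

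What is left without a clear duty is an uncomplicated pregnancy and the follow-up of its outcome.

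**The case against.** The strongest reply is that the text does not clearly close the window. Protocol 10.5.2.1 defines an on-treatment period that runs to 30 days after the last dose, and the Pregnancy Form sentence in 8.3 has no time limit. Both stand as reasons to call the wording ambiguous. Neither settles it. The 10.5.2.1 definition serves only to segment the safety analysis, 8.3 does not refer to it, and SAP 2.1.1 ends its own on-treatment period at the last administration. The Form sentence follows a paragraph that is limited to pregnancies on treatment.

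The exposure can also be put lower. At the stated 2-day half-life letrozole needs 10 days, and section 1.2.6 itself calls the observed accumulation consistent with about 2 days. Goserelin is part of study treatment and is given as a 28-day implant, so when treatment stops mid-cycle ovarian suppression still covers the days to the next due injection. That is fair, although a woman who stops at the end of a cycle does not have that cover.

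The Pregnancy Form, the Investigator's Brochure and the consent text could set a post-dose period. They were not available, and nothing is inferred from their absence.

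Two stronger readings are tempting.

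- Section 7.2.2.4.5 says that "during the study, and at the end of trial, urinary pregnancy tests are sufficient". A reader might infer that the study would detect pregnancies that it then need not report. The documents do not support this. The end-of-treatment visit falls within 7 days of stopping, so a positive test then would mostly reflect conception during dosing, which is reportable. The pregnancy-test row of Table 7-1 could not be read, so any later testing cannot be checked.
- Criterion 21 asks women for contraception while dosing, whereas 11.3 says that "they must adhere to the contraception requirement for the duration of the study". A reader might infer that women have no post-dose contraception cover. But end of study comes after the 30-day safety follow-up (4.3, 7.1.3.1), so 11.3 read naturally already includes it. This is inconsistent wording, not absent cover.

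**Conclusion.** The point holds as a minor gap in a stated safety rule. On its natural reading 8.3 makes no post-dose conception reportable. The documents' own half-lives leave drug present for roughly 10 to 16 days, and up to 23.7 days at one standard deviation above the letrozole mean. The rule is ambiguous, so it would be too strong to say that such a pregnancy could never have to be reported.

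The number affected is small. Cohort A holds only postmenopausal women and men, so the women concerned are essentially the pre- and perimenopausal part of cohort B. The documents give no count. Assuming 20% to 50% of the 150 planned, that is 30 to 75 women, fewer after those with permanent contraception. Goserelin makes conception unlikely. The clinical benefit rate and the sample size are unaffected.

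The conclusion rests on the five-half-life convention of 8.1.1 and on effective half-lives derived from accumulation, which are approximate. It does not depend on the exact day.

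**What to change.** In the first sentence of section 8.3, after the reference to being on study treatment, add: or within 30 days after the last dose of study treatment. State that the same form and outcome follow-up apply. Thirty days matches the AE and SAE windows and covers letrozole at +1 SD. The 21 days used for men would not, since 23.7 exceeds 21.

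Making the contraception wording of 11.3 and criterion 21 agree is optional. Enrolment is complete, so criterion 21 no longer screens anyone.

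The cost is one phrase and a slightly longer reporting duty for a small part of cohort B. The existing 30-day safety contact can carry it, with no new visit and no change to the analysis.

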8.4 Warnings and precautions

No evidence available at the time of the approval of this study protocol indicated that special warnings or precautions were appropriate, other than those noted in the provided Investigator Brochure. Additional safety information collected between IB updates will be communicated in the form of Investigator Notifications. This information will be included in the patient informed consent and should be discussed with the patient during the study as needed.

8.5 Steering Committee

A Study Steering Committee (SSC) will be constituted to oversee the conduct of the study and making any necessary recommendations as needed. The SC will ensure transparent management of the study according to the protocol through recommending and approving modifications as circumstances require. The SC will review protocol amendments as

appropriate. Together with the clinical trial team, the SC will also develop recommendations for publications of study results including authorship rules.

9 Data collection and management

9.1 Data confidentiality

Information about study subjects will be kept confidential and managed under the applicable laws and regulations. Those regulations require a signed subject authorization informing the subject of the following:

- What protected health information (PHI) will be collected from subjects in this study
- Who will have access to that information and why
- Who will use or disclose that information
- The rights of a research subject to revoke their authorization for use of their PHI.

In the event that a subject revokes authorization to collect or use PHI, the investigator, by regulation, retains the ability to use all information collected prior to the revocation of subject authorization. For subjects that have revoked authorization to collect or use PHI, attempts should be made to obtain permission to collect follow-up safety information (e.g. has the subject experienced any new or worsened AEs) at the end of their scheduled study period.

The data collection system for this study uses built-in security features to encrypt all data for transmission in both directions, preventing unauthorized access to confidential participant information. Access to the system will be controlled by a sequence of individually assigned user identification codes and passwords, made available only to authorized personnel who have completed prerequisite training.

9.2 Site monitoring

Before study initiation, at a site initiation visit or at an investigator's meeting, Novartis personnel (or designated CRO) will review the protocol and CRFs with the investigators and their staff. During the study, the field monitor will visit the site regularly to check the completeness of patient records, the accuracy of entries on the CRFs, the adherence to the protocol to Good Clinical Practice, the progress of enrollment, and to ensure that study treatment is being stored, dispensed, and accounted for according to specifications. Key study personnel must be available to assist the field monitor during these visits.

The investigator must maintain source documents for each patient in the study, consisting of case and visit notes (hospital or clinic medical records) containing demographic and medical information, laboratory data, electrocardiograms, and the results of any other tests or assessments. All information recorded on CRFs must be traceable to source documents in the patient's file. The investigator must also keep the original signed informed consent form (a signed copy is given to the patient).

The investigator must give the monitor access to all relevant source documents to confirm their consistency with the CRF entries. Novartis monitoring standards require full verification for the presence of informed consent, adherence to the inclusion/exclusion criteria and documentation of SAEs. Additional checks of the consistency of the source data with the CRFs are performed according to the study-specific monitoring plan.

9.3 Data collection

The designated investigator staff will enter the data required by the protocol into the Electronic Case Report Forms (eCRF). The eCRFs have been built using fully validated secure web-enabled software that conforms to 21 CFR Part 11 requirements, Investigator site staff will not be given access to the EDC system until they have been trained. Automatic validation programs check for data discrepancies in the eCRFs and, allow modification or verification of the entered data by the investigator staff.

The Principal Investigator is responsible for assuring that the data entered into eCRF is complete, accurate, and that entry and updates are performed in a timely manner.

Automatic validation procedures within the system check for data discrepancies during and after data entry and, by generating appropriate error messages, allow the data to be confirmed or corrected online by the designated investigator site staff. The Investigator must certify that the data entered into the electronic Case Report Forms are complete and accurate. After database lock, the investigator will receive copies of the patient data for archiving at the investigational site.

9.4 Database management and quality control

Novartis personnel (or designated CRO) will review the data entered by investigational staff for completeness and accuracy. Electronic data queries stating the nature of the problem and requesting clarification will be created for discrepancies and missing values and sent to the investigational site via the EDC system. Designated investigator site staff are required to respond promptly to queries and to make any necessary changes to the data.

Concomitant treatments and prior medications entered into the database will be coded using the WHO Drug Reference List, which employs the Anatomical Therapeutic Chemical classification system. Medical history/current medical conditions and adverse events will be coded using the Medical dictionary for regulatory activities (MedDRA) terminology.

The occurrence of relevant protocol deviations will be determined. After these actions have been completed and the database has been declared to be complete and accurate, it will be locked and made available for data analysis. Any changes to the database after that time can only be made by joint written agreement between the Trial Statistician and the Therapeutic Area Head.

10 Statistical methods and data analysis

The study is designed as an open-label, single-arm, phase IIIB trial to assess the efficacy and safety of ribociclib plus letrozole in women with hormone receptor positive advanced breast cancer.

The data will be analyzed by Novartis and/or designated CRO. Any data analysis carried out independently by the investigator should be submitted to Novartis before publication or presentation. It is planned that the data from participating centers in this protocol will be combined, so that an adequate number of patients will be available for analysis.

The data will be summarized with respect to demographic and baseline characteristics, efficacy observations and measurements, safety observations. The primary efficacy and safety analysis will be conducted on all patient data at the time all patients who are still receiving study drug will have completed at least 24 weeks of treatment (or discontinued prematurely). The additional data for any patients continuing to receive study drug past these

times, as allowed by the protocol, will be further summarized in a report once these patients complete the study.

In general, categorical variables will be summarized by absolute and relative frequencies. Continuous variables will be summarized by descriptive statistics (number of valid and missing observations, mean, standard deviation, minimum, median and maximum). Time-to-event data including rates of affected patients will be assessed using the Kaplan-Meier method. The primary aim of this trial is in estimation rather than significance testing of statistical hypotheses. Thus, mainly statistical estimators along with appropriate two-sided 95% confidence intervals will be used. However, changes from baseline may be explored using suitable statistical tests for paired samples. No adjustment for multiplicity is foreseen due to the exploratory nature of the trial.

